12.3 Sample Size/Accrual Rate

The planned sample size for this dose escalation Phase I study is between 6 and 24 total patients and the accrual for phase II will be between 16 and 27 patients and will include patients treated at the MTD from the phase I portion. The accrual rate is anticipated to be 1–2 subjects every month on average (with expected pauses in enrollment between dose-escalation cohorts and between the stage 1 and stage 2 of the phase II trial).

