| HIPAA | Health Insurance Portability and Accountability Act of 1996 |
| HRBAF | Human Research Billing Analysis Form |
| ICF | Informed Consent Form |
| IND | Investigational New Drug |
| IRB | Institutional Review Board |
| ¹⁷⁷Lu | Lutetium-177 |
| mCRPC | Metastatic Castration Resistant Prostate Cancer |
| MTD | Maximum tolerated dose |
| NA | Not Applicable |
| NCI | National Cancer Institute |
| PC | Prostate Cancer |
| PHI | Protected Health Information |
| PI | Principal Investigator |
| PSMA | Prostate Specific Membrane Antigen |
| ²²³Ra | Radium-223 |
| REDCap | Research Electronic Data Capture |
| RP2D | Recommended Phase 2 dose |
| SAE | Serious Adverse Event |
| SUSAR | Suspected Unexpected Serious Adverse Reaction |
| UAP | Unanticipated Problem |
| WCM | Weill Cornell Medicine |

Protocol Summary

| | |
|--------------------------------|--|
| Full Title: | Phase I/II dose-escalation trial of combination fractionated dose ^{177}Lu -J591 and ^{177}Lu -PSMA-617 in patients with metastatic castration-resistant prostate cancer |
| Short Title: | ^{177}Lu -J591 and ^{177}Lu -PSMA-617 combination for mCRPC |
| Clinical Phase: | Phase I |
| Principal Investigator: | [name], MS |
| Sample Size: | $N = 6 - 57$ (Phase I: 3 + 3 dose-escalation study design up to 6 dose-escalation / de-escalation cohorts for minimum of 6 and maximum of 30; Phase II minimum of 16 and maximum of 27) |
| Accrual Ceiling: | This study will enroll up to 57 subjects who receive treatment. |
| Study Population: | Adult male patients of ≥ 18 years with documented progressive metastatic CRPC |
| Accrual Period: | 3 years (approximately 1-2 patients per month with gaps between dose-escalation cohorts and between stage 1 and 2 of the phase II portion). |

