| Study Design: | Phase I dose escalation study with combination of ^{177}Lu -J591 and ^{177}Lu -PSMA-617 using a dose-fractionated regimen will be performed in patients with documented progressive metastatic CRPC. The cumulative ^{177}Lu-J591 dose for each subject will be 2.7 GBq/m² (73 mCi/m²) of ^{177}Lu with 20 mg J591 and the cumulative ^{177}Lu-PSMA-617 dose for each subject will vary (depending on the Cohort) from 3.7 GBq (100 mCi) to 18.5 GBq (500 mCi). The ^{177}Lu -PSMA-617 dose will be escalated in up to 6 different dose levels (3+3 dose-escalation study / de-escalation design). For the phase II portion, a minimum number of 14 patients will be enrolled at MTD (including those enrolled at MTD in Phase I) and a maximum of 24. |
| Study Duration: | Approximately 3 months after enrollment, then transition to long-term follow up |
| Study Agent: | 1) ^{177}Lu -PSMA-617 [1.85 GBq (50 mCi) – 9.25 GBq (250 mCi)] x2 doses, 2 weeks apart (Treatment Visit #1 and #2), IV administration 2) ^{177}Lu -J591 [1.35 GBq/m ² or 36.5 mCi/m ²] x2 doses, 2 weeks apart (Treatment Visit #1 and #2), IV administration 3) ^{68}Ga -PSMA-HBED-CC [185 \pm 74 MBq or 5 \pm 2 mCi] intravenous during screening and at 12 weeks (\pm 1 week) with standard imaging |
| Primary Objectives: | 
(Phase I) Determine the dose limiting toxicity (DLT) of dose-fractionated combination therapy with ^{177}Lu-J591 and ^{177}Lu-PSMA-617 |

- (Phase I) Determine the maximum tolerated dose (MTD) and recommended phase II dose (RP2D) of dose-fractionated combination therapy with ^{177}Lu -J591 and ^{177}Lu -PSMA-617
 - (Phase II) To assess the proportion with PSA decline following the dose-fractionated combination therapy with ^{177}Lu -J591 and ^{177}Lu -PSMA-617
- Secondary Objectives:**
- To assess radiographic response rate by RECIST 1.1 with PCWG3 modifications
 - To assess biochemical and radiographic progression-free survival by PCWG3 criteria
 - To assess overall survival following the dose-fractionated combination therapy with ^{177}Lu -J591 and ^{177}Lu -PSMA-617
 - To assess safety of dose-fractionated combination therapy with ^{177}Lu -J591 and ^{177}Lu -PSMA-617 as assessed by CTCAE 4.0
 - To assess changes in CTC count as measured by CellSearch and the rate of favorable CTC count and LDH at 12 weeks following dose-fractionated combination therapy with ^{177}Lu -J591 and ^{177}Lu -PSMA-617

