| | Dose: GBq (mCi) / m ² | Dose: GBq (mCi) |
| Cohort | | |
| -1 | 2.22 (60) | 1.85 (50) |
| 1 | 2.22 (60) | 3.7 (100) |
| 1a | 1.35 (36.5) | 3.7 (100) |
| 2 | 1.35 (36.5) | 5.55 (150) |
| 3 | 1.35 (36.5) | 7.4 (200) |
| 4 | 1.35 (36.5) | 9.25 (250) |

*Note: BSA will be capped at 2 for ¹⁷⁷Lu-J591 dosing.

Rationale for dosing amendment:

Prior studies of ¹⁷⁷Lu- and ⁹⁰Y-J591 have utilized individualize dosing per body surface area (BSA). As a single agent, ¹⁷⁷Lu-J591 when delivered in a 2-dose fractionated regimen is suggested to be dosed at 45 mCi/m² x2 (or 40 mCi/m² x2 with less toxicity and less efficacy). The dose in combination with docetaxel is 40 mCi/m² x2). In the initial version of the protocol, an estimate for fixed dosing based upon prior safe dose levels and average BSA was utilized. One subject in the initial cohort had prolonged myelosuppression and on analysis, had a low BSA. Therefore based upon the wealth of prior safety data with BSA dosing and the wish to primarily assess one rather than 2 dosing variables, the dosing amendment will revert to BSA dosing. In addition, we will cap BSA at 2 m² with the intent of minimizing myelosuppression from the RIT.

4.2 Phase I:

The Phase I portion will use a 3+3 dose-escalation study design, with the planned initial and subsequent cohorts described in Table 14. This study design is well-described and accepted by the clinical and scientific community, so we will not provide complete details here. Briefly, this design is constructed to reduce the chance of escalating the dose when the probability of DLT is high, and increase the chance of escalating the dose when the probability of DLT is low. The MTD is defined as the highest dose level with an observed incidence of DLT in no more than one out of six patients treated at a particular dose level. The dose escalation scheme provides the following probabilities of escalation based on the true chances of DLT at a specific dose level. One can see that the probability of escalation is high if the toxicity risks are low:

| | | | | | | | |
|-------------------------------|-----|-----|-----|-----|-----|-----|-----|
| True Probability of Toxicity: | .05 | .10 | .20 | .30 | .40 | .50 | .60 |
| Probability of Escalation: | .97 | .91 | .71 | .49 | .31 | .17 | .08 |

As there is a reasonably large pool of short- and long-term experience with PSMA-directed ¹⁷⁷Lu, a phase II trial using the MTD to will be launched to obtain preliminary efficacy data.

4.3 Phase II:

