6.2.4 Dose levels for ^{177}Lu -J591 + ^{177}Lu -PSMA-617

Subject(s) enrollment will be done as 3+3 study design at each dose level. Initially at least 3 subject(s) will be enrolled in Cohort 1 and will receive ^{177}Lu -PSMA-617 (2 GBq or 54 mCi x2 doses 2 weeks apart) with dose escalation as described above in **Section 4.1 (Table 14)**.

Simultaneously, all subjects will receive in combination a fixed dose of ^{177}Lu -J591 (1.35 GBq/m² or 36.5 mCi/m² capped at BSA of 2) x2 doses, 2 weeks apart. The enrollment ceiling of the dose escalation portion of the study is up to 30 treated study participants (up to five groups, up to 6 at each dose level). Each patient would receive two doses of both investigational agents (^{177}Lu -J591 and ^{177}Lu -PSMA-617) in combination 2 weeks apart. The total dose received by a subject will vary from **4 GBq/m² (108 mCi/m²) to 20 GBq/m² (540 mCi/m²)** for ^{177}Lu -PSMA-617. The total dose received by a subject for ^{177}Lu -J591 will be **2.7 GBq/m² (73 mCi/m²)**, with BSA capped at 2.

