12.2. Phase II Study Design/Endpoints

We will enroll up to 27 subjects into the Phase II portion (including the 3-6 used for establishing the MTD). We will define evaluable patients as patients who met eligibility requirements, have initiated therapy, and were not removed from the study for non-compliance or patient withdrawal.

Sample size recommendations for the two-stage design are determined according to Simon's two-stage minimax design. We project a 30% PSA decline proportion of 35%, below which the regimen will be unacceptable and a 30% PSA decline proportion of 60%, above which the regimen will be considered worthy of further exploration. The null hypothesis that the 30% PSA decline proportion is less than or equal to 35% will be tested against the alternative hypothesis that the 30% PSA decline proportion is greater than or equal to 60%.

The sample size computations were performed assuming a 0.10 one-sided level of significance and 90% power assuming a historical control value for PSA decline of 35% and the alternative

hypothesis of 60%. If 6 or fewer of the first 16 evaluable patients do not experience a 30% decline in PSA (stage 1), the study will be terminated and declared to have a negative result. If 7 or more patients out of the first 16 evaluable patients experience a 30% decline in PSA, ongoing accrual will proceed to the target sample size of 27 patients (stage 2). The new regimen will be declared active in this patient population and worthy of further testing if 13 or more patients experience a 30% PSA decline among the 27 patients entered. This two-stage design yields a 0.90 probability of a positive result if the true 30% PSA decline proportion is 60%. It yields a 0.90 probability of a negative result if the true 30% PSA decline proportion is 35%. An exact 95% binomial confidence interval will be constructed for the proportion of patients with PSA decline.

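### The Phase I maximum is 24 in one section and 30 in two others, and the ceiling of 57 counts the patients treated at the MTD twice unless Phase I can reach 36

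*Combined protocol and SAP*

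**What the plan says.** Four places set the size of Phase I or of the whole trial.

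- Section 12.3 (Sample Size/Accrual Rate): "The planned sample size for this dose escalation Phase I study is between 6 and 24 total patients".
- Protocol Summary, Sample Size row: "up to 6 dose-escalation / de-escalation cohorts for minimum of 6 and maximum of 30; Phase II minimum of 16 and maximum of 27". The Study Design row adds that the PSMA-617 "dose will be escalated in up to 6 different dose levels".
- Section 6.2.4, given as the enrollment ceiling of the escalation portion: "up to 30 treated study participants (up to five groups, up to 6 at each dose level".
- Protocol Summary, Accrual Ceiling row: "This study will enroll up to 57 subjects who receive treatment".

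The dose-escalation table in Section 4.1 lists six cohorts: -1, 1, 1a, 2, 3 and 4. The text of Section 4.1 opens Cohort -1 only after unacceptable toxicity at the initial level.

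On the overlap between phases, Section 12.2 sets Phase II at up to 27 subjects, "including the 3-6 used for establishing the MTD". Sections 4.3 and 12.3 likewise count the Phase I patients treated at the MTD within Phase II.

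**The concern.** These figures limit how many men may be treated, and they do not agree.

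First, 24 and 30 are both printed as the Phase I maximum. Second, the same 30 is attached to up to six cohorts in one place and to five groups in another. Third, the ceiling adds the two phase maxima as if no patient belonged to both, while three sections say that some do.

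A low Phase I figure, if enforced, could cut escalation short for an administrative reason. A high total authorises more treated patients than the printed phase maxima can use.

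**Working it through.** **Inputs.** Phase I maximum: 24 (Section 12.3) or 30 (Protocol Summary, Section 6.2.4). Cohort size: up to 6 (Section 6.2.4). Phase II maximum: 27, including the MTD patients (Sections 4.3, 12.2, 12.3). Ceiling: 57 (Protocol Summary).

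**1. Reproducing the plan's ceiling.** 30 + 27 = 57, with no overlap removed. Section 12.3's own figure gives 24 + 27 = 51 by the same plain sum.

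**2. Phase I maximum by cohort count, at six per cohort.** 4 × 6 = 24; 5 × 6 = 30; 6 × 6 = 36. The 30 fits five groups (Section 6.2.4) but not six full cohorts. The 24 fits four full cohorts.

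**3. Distinct patients.** Let *k* cohorts open, with *m* patients in the MTD cohort and six in each of the others. Phase I holds 6(*k* − 1) + *m*. The *m* MTD patients also sit inside the 27, so

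distinct total = 6(*k* − 1) + *m* + 27 − *m* = 6(*k* − 1) + 27.

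The *m* cancels, so the maximum is the same whether the MTD cohort holds three or six.

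| Cohorts opened | Phase I maximum | Plain sum with 27 | Distinct patients |
|---|---|---|---|
| 4 | 24 | 51 | 18 + 27 = 45 |
| 5 | 30 | 57 | 24 + 27 = 51 |
| 6 | 36 | 63 | 30 + 27 = 57 |

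With a Phase I maximum of 30, the ceiling exceeds the distinct maximum by 57 − 51 = 6.

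**4. How often a cap of 24 would bind.** Suppose Cohort 1 used six patients. Cohorts 1a, 2 and 3 at six each then bring the count to 24, and nothing is left for Cohort 4. Assume the same DLT rate *p* at every level and standard 3+3 rules. Per cohort, let *a* = (1 − *p*)³ (escalate after three), *e* = 3*p*(1 − *p*)⁵ (escalate after six) and *x* = 3*p*(1 − *p*)² (expand from three to six).

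- Cohorts 1a, 2 and 3 all use six and all escalate, so Cohort 4 cannot open: *e*³. This is 0.16% at *p* = 0.05, 0.80% at 0.15 and 0.56% at 0.25.
- More than 24 needed at any point, with no extra filling of the MTD cohort: *e*³ + 3*e*²*ax*. This is 0.6% at 0.05, 3.2% at 0.15 and 2.3% at 0.25.
- The same, but with the MTD cohort filled to six (simulation, 40,000 runs per rate): 4.0% at 0.05, peaking at about 10% at 0.15.
- If Cohort 1 used only three patients: *e*³*x* without filling, which is 0.02% at 0.05 and 0.26% at 0.15. With filling it is at most about 1%.

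The documents do not say how many patients Cohort 1 used, so both cases are assumptions.

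**5. Phase II.** An exact binomial check of the stated rule (continue with 7 or more of 16, success with 13 or more of 27) gives a one-sided alpha of 0.098 at a 35% response proportion and power of 0.900 at 60%. A search returns the same design as the minimax solution. Nothing in steps 1 to 4 alters these values.

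**The case against.** Much can be said for reading the figures generously.

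*Six cohorts need not mean 36.* Cohort -1 is a de-escalation branch. The upward path 1, 1a, 2, 3, 4 has five cohorts, which gives exactly 30 and agrees with Section 6.2.4. The Protocol Summary's six can be read as six possible levels with at most 30 patients among them. This stands: 36 is derived, and a reader should not treat it as a third stated maximum. It does not rescue the 24.

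*The 24 is called a planned size.* The places worded as ceilings are the Protocol Summary and Section 6.2.4, and neither uses 24. This makes enforcement of 24 less likely. It does not remove the conflict, because 24 stands in the section that defines the sample size.

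*The extra six may be an allowance.* The ceiling counts treated subjects, while the stage 1 rule counts evaluable ones. Section 12.6.2 leaves replacement of non-evaluable patients open. Treated patients could therefore exceed evaluable ones. But no section says that 57 contains such a margin, and Section 12.2 also speaks of the 27 as patients entered. The possibility needs a sentence in the plan.

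A reader might also subtract only three MTD patients and put the maximum at 30 + 27 − 3 = 54. That case cannot occur: a Phase I total of 30 needs six in every cohort, including the one at the MTD. With three there, Phase I reaches at most 27, and 27 + 27 − 3 is again 51.

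**Conclusion.** The conflict is real and stands in current text. The printed contradiction is 24 against 30 for Phase I. The ceiling of 57 matches the printed 30 and 27 only if the shared patients are counted twice. Counted once, 30 and 27 give 51. A ceiling of 57 is right only if all six cohorts can open and fill, which no section states.

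The consequence is modest. A reader might infer that the 24 would commonly block the top dose level. The documents do not support that: even with six patients used in Cohort 1, the cap is exceeded in roughly 1–10% of trials, and Cohort 4 is shut out completely in under 1%. Those percentages rest on a constant DLT rate of 5–25% per level, on the assumed size of Cohort 1, and on whether the MTD cohort is filled to six. A reader might also infer that the Phase II error rates suffer. They do not, because the 16/27 design is untouched by the Phase I figures or by the ceiling.

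**What to change.** Decide how many cohorts can open, and use one set of numbers in the Protocol Summary, Section 6.2.4 and Section 12.3.

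- If at most five can open: Phase I 6–30 (changing Section 12.3) and a ceiling of 51 distinct treated patients.
- If all six can open: a Phase I maximum of 36 and a ceiling of 57.

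Say in the ceiling row that patients treated at the MTD are counted once. If the ceiling is meant to cover replacement of non-evaluable patients, state the number allowed and add it openly, because a ceiling of 51 leaves no room for replacements if every cohort fills.

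In the same edit, reconcile the Phase II range of 14 to 24 in the Study Design row of the Protocol Summary with the 16 to 27 given elsewhere. Also correct the stage 2 increment: Sections 4.3 and 12.6 add 9 patients to 16, which makes 25, whereas 27 needs 11.

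The cost is wording. No design parameter, decision rule or analysis changes.

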12.4 Stratification Factors

This is not a randomized trial and so there are no stratification factors.

12.5 Analysis of Endpoints

12.5.1 Analysis of Primary Endpoints

The primary endpoint will be the proportion of subjects with DLT from Treatment Visit #1 through End of Study (Efficacy/scan) Visit. The MTD is the highest dose amongst the different dose-level cohorts in this study at which no more than 1 out of 6 subjects in a cohort experience DLT.

12.5.2 Analysis of Secondary Endpoints

For PSA response, CTC response and imaging response, descriptive analysis will be done. For imaging response RECIST (Version 1.1) criteria with PCWG3 modifications will be applied. Biomarker and patient reported outcome data will be analyzed within this study as well as across additional radiolabeled-PSMA studies.

12.6 Interim Analysis

No interim analysis is planned for the phase I portion (though safety analyses will occur in real-time and prior to each dose-escalation). For the phase II portion, accrual will be suspended

after 16 patients have been enrolled in stage 1. If at least 7 patients out of the 16 patients experienced a PSA decline > 30%, 9 more patients will be accrued as part of stage 2.

12.6 Reporting and Exclusions

12.6.1 Evaluation of toxicity

All subjects will be evaluable for toxicity from the time of their first infusion with ⁶⁸Ga-PSMA-HBED-CC as well as when they receive their first treatment with ¹⁷⁷Lu-J591 + ¹⁷⁷Lu-PSMA-617 and up to 30 days after their last treatment. The distributions of the maximum observed grade toxicity will be tabulated for each type of toxicity and presented by dose level and overall. Results will be summarized with descriptive statistics.

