6. STUDY PROCEDURES

Screening assessments and study procedures outlined in this section can only be performed after obtaining informed consent. All on-study visits and dosing should be scheduled from Day 1 (date of the first infusion) on the study. It is very important that protocol procedures are performed at the time-points stipulated below. When it is not possible to perform, the study visit at the exact time-point, the visit maybe performed within the acceptable visit window as defined in the visit-specific section below.

After obtaining informed consent from enrolled subject(s), screening and study related treatment procedures will be performed as outlined in **Table 15** and described in detail in **Section 6.1**.

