- c: Any subject with grade ≥2 neutropenia or thrombocytopenia at Treatment 2 will initially not be eligible to receive the second ¹⁷⁷Lu-J591 / ¹⁷⁷Lu-PSMA-617 infusions. The dose will be held until the toxicity has resolved to grade 1 for a maximum of 2 weeks. If the toxicity has not resolved after 2 weeks, the dose will be discontinued.
- d: CMP (with direct bilirubin in subjects with known Gilbert’s syndrome)
- e: CTC enumeration via CellSearch methodology may be obtained during screening or prior to treatment C1D1
- f: CTC collection for research purposes may be performed during screening or prior to treatment C1D1: two 2.3% sodium citrate “light blue top” tubes
- g: Cell-Free DNA BCT[®] may be obtained during screening or prior to treatment C1D1 and will be whole blood collection in a tube intended for collection, stabilization and transportation of cell-free plasma DNA. 10 mL tube will be used for collecting whole blood for research purposes
- h: Radiographic evaluation will include bone scan, CT/MRI of abdomen/pelvis, and Chest x-ray (CXR waived if CT/MRI includes chest). Following mandatory repeat imaging with Scan/Efficacy visit, continued repeat imaging is recommended approximately 12 weeks until radiographic progression as part of standard care.
- i: Planar/SPECT imaging one week after the ¹⁷⁷Lu-PSMA-617 1st dose infusion in all subjects. Optional imaging will be performed on consenting subjects between D1-D4 and/or prior to treatment #2 on D15.
- j: Survival assessment and relevant medical history to be collected until death
- k: Short-term follow up to be completed q4 weeks following the scan visit until 6 months from the 1st treatment visit. Subjects who are progression-free at 6 months will continue with q4-week labs and q12-week standard imaging per guidelines (as in h above).
- l: PRO = patient reported outcomes = BPI-SF and FACT-P; to be performed at time points specified during treatment phase, then q12 weeks (at imaging time points) during short-term follow up until radiographic progression
- m: serum for immune assays; 1 sample to be collected at any time during screening prior to treatment #1, then again during scan/efficacy visit

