6.1.1. Screening Visit

The following procedures must be completed no more than 1 month prior to enrollment and no more than 4 weeks following enrollment.

- Informed Consent
- Demographics
- Medical History
- Previous therapy
- Surgical report will include date and type of surgery +/- lymphadenectomy
- Radiotherapy report will include modality of therapy with prescribed dose and field and dates of therapy
- Previous systemic (hormonal, chemo, other) therapy – drugs, doses, dates of therapy
- Complete Physical Exam including height and weight
- Brief Pain Inventory
- Vital Signs
- ECOG Performance Status
- CBC with differential and platelet count
- CMP (with direct bilirubin with known Gilbert's syndrome)
- PSA
- Testosterone
- CTC count via CellSearch methodology (may be collected prior to treatment C1D1, do not need to repeat if has known result within 1 month of C1D1)
- CTC for Research (may be collected prior to treatment C1D1)
- Cell-Free DNA BCT[®] Research blood sample (may be collected prior to treatment C1D1)
- Immune research blood sample (may be collected prior to treatment C1D1)
- CT or MRI (abdomen-pelvis), up to 1 month prior to enrollment
- Bone scan, up to 1 month prior to enrollment
- Any confirmatory tests to assess equivocal results of bone scan should also be completed within a month of enrollment
- CXR, up to 1 month prior to enrollment (CXR waived if CT chest performed)
- Single intravenous dose of ⁶⁸Ga-PSMA-HBED-CC (5±2mCi or 185±74MBq) at least 1 week prior to ¹⁷⁷Lu-PSMA-617 infusion
- ⁶⁸Ga-PSMA-HBED-CC PET/CT scan to confirm the PSMA expression at the tumor site(s). PET/CT scans will be obtained 1 to 3 hours after the infusion of ⁶⁸Ga-PSMA-HBED-CC
- Archival tissue for PSMA expression and genomic studies to identify DNA damage

Screening (except ^{68}Ga -PSMA-HBED-CC PET/CT scan) and visit #1 may occur on the same day provided results are available, all entry criteria are met, and the subject is registered on the study prior to dosing. In this instance, duplicate procedures do not need to be performed.

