- PSA (Follow up visits 2 & 4)
- LDH (Follow up visits 2 & 4)
- Adverse event evaluation
- Concomitant medications

6.1.2.3 Follow-up lab visits: Follow up Visit 3 (Day 43 \pm 3); Follow up Visit 5 (Day 71 \pm 3)

- CBC with differential and platelet count
- CMP (with direct bilirubin with known Gilbert's syndrome)
- PSA
- LDH

Lab visits may be performed at any CLIA certified lab

6.1.3. Efficacy Evaluation (scan) Visit (Day 85 ± 7; note that these study procedures are not expected to occur on a single day)

The following procedures must be completed during the efficacy visit(s):

- Targeted Physical Examination with vital signs and weight
- Medical History
- Brief Pain Inventory, FACT-P
- ECOG Performance Status
- CBC with differential and platelet count
- CMP (with direct bilirubin with known Gilbert's syndrome)
- PSA
- LDH
- Testosterone
- CTC count via CellSearch methodology
- CTC for research
- Cell-Free DNA BCT[®] Research blood sample
- Immune research blood sample
- Same standard radiographic imaging modality as baseline (CT/MRI and bone scan +/- CXR)
- Single intravenous dose of ⁶⁸Ga-PSMA-HBED-CC (5±2mCi or 185±74MBq)
- PET/CT scan will be obtained between 1 and 3 hours post-injection of ⁶⁸Ga-PSMA-HBED-CC
- Adverse event evaluation
- Concomitant medications
- Concomitant procedures

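### The maximum-grade toxicity table appears to close 30 days after the last treatment (about Day 45 on schedule), while DLTs are counted to Day 85 ± 7, so a late worst grade could be missing from the table for its dose level

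*Combined protocol and SAP*

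**What the plan says.** Section 12.6.1 (Evaluation of toxicity) stands under the heading on reporting and exclusions. Subjects are evaluable for toxicity from their first 68Ga infusion and from their first 177Lu treatment "and up to 30 days after their last treatment". The following sentence defines the output: "The distributions of the maximum observed grade toxicity will be tabulated for each type of toxicity and presented by dose level and overall". It gives no separate cutoff for that table.

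Section 12.5.1 sets a different end-date for the Phase I primary endpoint: "The primary endpoint will be the proportion of subjects with DLT from Treatment Visit #1 through End of Study (Efficacy/scan) Visit". Section 6.1.3 places that visit: "Efficacy Evaluation (scan) Visit (Day 85 ± 7" days. The DLT definition in section 6.2.10 carries no day limit of its own.

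The second 177Lu dose is due on Day 15 ± 1 (section 6.1.2.1). It may be delayed for low counts; footnote c to Table 15 says "The dose will be held until the toxicity has resolved to grade 1 for a maximum of 2 weeks", after which it is not given. A delay to dose 2 does not move the later visits, because section 6 says: "All on-study visits and dosing should be scheduled from Day 1 (date of the first infusion) on the study".

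No section reconciles the two end-dates.

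**The concern.** Safety is a secondary objective, and 12.6.1 specifies the toxicity table by dose level. If that table follows the evaluability window stated just before it, it closes well before the DLT window. A DLT first seen in between would count toward the MTD under 12.5.1 yet could be absent from the toxicity table for the same dose level. The same applies to a late worst grade that is not a DLT, and such an event has no primary-endpoint count to bring it back into view. For post-treatment events, the table could then understate worst grade at a dose level.

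The position of the cutoff makes this more than a formality. Section 2.8 expects red marrow to be the dose-limiting tissue for 177Lu-J591, and the marrow nadir reported in section 2.7 falls around the day on which evaluability ends.

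**Working it through.** The plan gives no figure for this gap, so there is none to reproduce. The check is day arithmetic.

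**Inputs**
- Dose 1: Day 1. Dose 2: Day 15 ± 1, that is Day 14 to 16 (6.1.2.1).
- Longest hold for low counts: 14 days (Table 15, footnote c).
- End of toxicity evaluability: last treatment + 30 days (12.6.1).
- End of DLT window: Day 85 ± 7, that is Day 78 to 92 (12.5.1 with 6.1.3).
- Neutrophil and platelet nadir in the earlier J591 studies: 28 to 32 days after the last 177Lu-J591 dose (2.7, part B).

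**Formula.** With L the day of the last 177Lu treatment, evaluability ends on L + 30. The gap is the Efficacy/scan visit day minus (L + 30).

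| Dosing | L | L + 30 | Gap to Day 85 | Range over visit windows |
|---|---|---|---|---|
| Both doses on schedule | 15 (14–16) | 45 (44–46) | 85 − 45 = 40 days | 78 − 46 = 32 to 92 − 44 = 48 |
| Dose 2 after a full two-week hold | 15 + 14 = 29 (28–30) | 59 (58–60) | 85 − 59 = 26 days | 78 − 60 = 18 to 92 − 58 = 34 |
| One dose only | 1 | 31 | 85 − 31 = 54 days | 78 − 31 = 47 to 92 − 31 = 61 |

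The table window closes before the DLT window in every case.

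**Nadir against cutoff.** For a Day 15 dose, the nadir falls between 15 + 28 = Day 43 and 15 + 32 = Day 47, on either side of Day 45. Some worst counts would be expected just before the cutoff and some just after it. Take a subject at grade 3 on Day 43 who reaches grade 4 a week later. Footnote b to Table 15 requires at least weekly follow-up above grade 2, so the grade 4 value would be seen. It would be a DLT if at least possibly related (6.2.10). On the natural reading of 12.6.1, the table could still show grade 3.

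**What 'last treatment' means.** If it included the 68Ga injection at the Efficacy/scan visit, evaluability would end on about Day 85 + 30 = 115 (78 + 30 = 108 to 92 + 30 = 122), and there would be no conflict. The wording of 12.6.1 points the other way: it calls 68Ga an infusion and the 177Lu combination the treatment.

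**The case against.** The strongest reply is that the loss is inferred. 12.6.1 says when subjects are evaluable, then tabulates the maximum observed grade; it does not tell the analyst to discard a grade recorded on Day 57. That is correct, and it is why the point is that a late grade could be missing, not that it will be. The cutoff nevertheless comes immediately before the table sentence, under a heading about exclusions, and no other end-date is offered. An analyst following the text would most naturally apply it.

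The second reply is that late events are still captured and reported elsewhere. This also stands. REDCap collects all toxicity data (11.1), adverse events are followed until they resolve or stabilise (13.3), and safety is reviewed before each escalation (12.6, Interim Analysis). The DSMB receives adverse event tables (14). Section 12.1 also allows other descriptive summaries or subject listings, so the maximum-grade table is not the only planned safety output.

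Several stronger readings are tempting, but the documents do not support them:
- **That MTD decisions could miss late DLTs.** 12.5.1 has its own window through the Efficacy/scan visit.
- **That a count of scheduled visits after the cutoff measures the loss.** Footnote b adds at least weekly follow-up for subjects above grade 2 neutropenia or thrombocytopenia, and section 4.1 gives a different adverse event schedule from Table 15.
- **That every DLT in a one-dose subject is at risk.** Failure to recover within the two-week hold is itself a DLT, reached about Day 15 + 14 = 29, before Day 31. Only a later worsening could fall outside.
- **That the differing start-dates are an error.** Toxicity evaluability opens at the screening 68Ga infusion, and 12.5.1 opens at Treatment Visit #1. Since 6.2.10 lets 68Ga-related toxicity count as a DLT, the earlier start is a defensible choice that adds events.

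**Conclusion.** The two end-dates conflict and should be reconciled. Toxicity evaluability closes about 40 days before the DLT window on schedule, 26 days before it after a full hold, and 54 days before it with one dose. A DLT or other worst-grade toxicity first seen in that interval could be missing from the maximum-grade table for its dose level.

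This rests on two readings: that the table uses the evaluability window stated just before it, and that the last treatment means the last 177Lu dose. Both are natural readings of 12.6.1, but neither is explicit. The nadir figure comes from earlier 177Lu-J591 studies, not from this combination, so it shows where late worst grades are plausible and not how many there will be. That share cannot be computed from the documents.

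The consequence is confined to one descriptive table. It deserves correction because that table reports toxicity by dose level and could disagree with the trial's own DLT count.

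**What to change.** In 12.6.1, replace the limit "and up to 30 days after their last treatment" with this end-date: through the Efficacy/Scan visit (Day 85 ± 7), or 30 days after the last treatment if later; for subjects who leave earlier, through their last safety assessment. Add a sentence stating that the maximum-grade table by dose level uses this end-date.

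The 'if later' clause is a safeguard. None of the three dosing patterns reaches it (latest Day 60 against earliest Day 78); it would apply only after a long logistical delay of the kind section 7 allows the study chair to clear.

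The cost is about two sentences. The blood counts and adverse event assessments are already scheduled through the Efficacy/scan visit, and no dose, visit or clinical rule changes. The downside is that reported toxicity may look slightly less favourable, and the longer window may take in more disease-related events.
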